12.3 Final Analysis

Descriptive statistics including measures of central tendency, dispersion and appropriate visualization approaches (e.g., box plots and spaghetti plots) will be performed on each outcome variable (pain scores, and outcomes in secondary and exploratory objectives) by time points and groups. This will be done to ascertain distributional characteristics and ensure that the assumptions (e.g., normality) associated with the planned statistical procedures are met. When necessary, transformations will be performed. All analyses will be done in SAS and will follow an intent-to-treat philosophy.

The main goal of the statistical analyses is to compare the changes in study primary and secondary endpoints between groups to evaluate efficacy of Erenumab. For the primary objective, the generalized Linear Mixed Models (GLMM) with binomial distribution will be used to assess the efficacy of Erenumab on the primary endpoint (i.e., at least 30% reduction in pain score; yes/no). The fixed effects included in the models will be treatment group (intervention versus placebo), time (dummy coded from baseline to visits 2-4), and the interaction terms of group by time. The random effects include the participants to account for correlations between repeated measures. The primary hypothesis will be tested by evaluating the interaction term of group and time from baseline to visit 4. In the meantime, the Erenumab efficacy from baseline to visits 2 and 3 will be evaluated through the interaction terms at the corresponding time points. The secondary objective of the difference in change (>30% reduction) from baseline to visit 5 will also be evaluated using the similar GLMM model with the corresponding time (baseline, V2-V5), group and interaction terms between time and group. The interaction of time (baseline to V5) and group will be evaluated to test the hypothesis. The difference from V4 to V5 will also be evaluated by contrast estimation from the model. We will use a significance level of twosided α < 0.05 as primary hypothesis test.

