Separate linear mixed models will be applied to test other secondary objectives (e.g., monthly mean pain scores, measures of daily activities and functions, etc.) and exploratory objectives (e.g., QST measures) where the outcome variables are continuous. The model and testing will be the same as described in the above primary objective. The use of mixed models will provide flexibility with regard to assumptions related to the covariance structure of the residuals and the presence of missing data for the repeated measures.

Descriptive statistics for safety measures will also be calculated. We will collect the following data for descriptive purposes and, if necessary, to use as covariates: Demographic information (age and race/ethnicity), rescue medication history, psychological factors and perceived change in overall status (PGIC).

Missing Data

Participants may miss specific data points for a variety of reasons such as a missed visit, early withdrawal from the study, or inability to evaluate an endpoint at a time point. If participants miss entering data in the DSD, the missing data will be imputed by the mean of observed daily data if the missing days are less than 80% within a month. If the missing days are more than 80%, the monthly measurement from the previous month will be carried forward to replace the missing value for continuous endpoints.

If there is significant dropout, we will identify baseline characteristics that differ between those dropped out and retained. Maximum likelihood methods will be used for primary analyses, which address non-informative dropout [missing at random (MAR)]. If "informative" dropout is present, we will consider sensitivity analyses that add these relevant baseline covariates to make the MAR assumption more plausible [50]

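### The continuous repeated-measures models name only a participant random effect and choose no residual covariance; fitted as written, the baseline-to-Visit-4 test can be anti-conservative

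*Combined protocol and SAP*

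**What the plan says.** Section 12.3 (Final Analysis) describes the primary model as a generalized linear mixed model with group, categorical time (baseline and Visits 2 to 4) and their interaction. On correlation it says: "The random effects include the participants to account for correlations between repeated measures". The test is also stated: "The primary hypothesis will be tested by evaluating the interaction term of group and time from baseline to visit 4".

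The Visit 5 responder objective is analysed "using the similar GLMM model with the corresponding time (baseline, V2-V5), group and interaction terms between time and group".

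For monthly mean pain, the functional scales and the continuous exploratory measures, the plan uses separate linear mixed models and says "The model and testing will be the same as described in the above primary objective". It adds that mixed models offer "flexibility with regard to assumptions related to the covariance structure of the residuals". It names no residual structure, rule for choosing one, robust standard error or degrees-of-freedom method.

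The 5% level is set for the primary test: "We will use a significance level of twosided α < 0.05 as primary hypothesis test". It reaches the continuous outcomes only through the sentence that carries the testing over.

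**The concern.** A participant intercept with independent residuals implies one variance for every month and one correlation for every pair of months. Every month-to-month change then has the same variance, which the model estimates by pooling over all pairs. The tested contrast, baseline to Visit 4, spans the longest interval in the four-point model. If months further apart are less correlated, that change varies more than the pooled estimate implies, so its standard error and p-value are too small. The same happens without smooth decay if the start of dosing at Visit 1 separates baseline from the later months.

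Reduction in monthly mean pain to the end of treatment is the first secondary objective in section 3.1, and the functional scales are also secondary. This pilot is meant to lay the ground for further CGRP-targeted treatment, so an overstated result on the main continuous pain measure could misdirect later work.

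**Working it through.** **Inputs from the plan.** 40 participants, 20 per arm, with 15% dropout, so 40 × 0.85 = 34 completers or 17 per arm (section 12.2). Four time points, categorical time, participant random effect, two-sided 0.05 (section 12.3).

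**Inputs that are assumptions.** All correlations and relative SDs between months; the documents give none for pain scores or questionnaires.

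**Method.** With complete balanced data, the REML interaction test from a random-intercept model is the split-plot analysis-of-variance test.

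- Variance ratio: r = Var(V4 − baseline) / [2 × (mean variance − mean covariance)].
- Actual two-sided error: 2 × [1 − Φ(1.96/√r)].

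With equal variances, four time points and correlations c1, c2, c3 at lags 1, 2 and 3, this becomes r = (1 − c3) / [1 − (3c1 + 2c2 + c3)/6].

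**The plan's own figure.** With equal correlation r = 1 and the error is 0.050. Null simulation (50,000 trials per setting) gave 0.051 at 20 per arm and 0.050 at 17.

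**Worked example, correlations .80/.75/.70.** Mean correlation = (2.40 + 1.50 + 0.70)/6 = 0.767. r = 0.30/0.233 = 1.29. 1.96/√1.29 = 1.73, so the error is 0.084.

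**Four time points, random intercept only:**

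| Assumed pattern | r | Error by formula | Simulated, 20 per arm |
|---|---|---|---|
| Equal correlation | 1.00 | 0.050 | 0.051 |
| Lags .80/.75/.70 | 1.29 | 0.084 | 0.083 |
| Lags .80/.70/.60 | 1.50 | 0.110 | 0.110 |
| AR(1) 0.3 | 1.19 | 0.073 | 0.072 |
| AR(1) 0.5 | 1.35 | 0.092 | 0.094 |
| AR(1) 0.7 | 1.53 | 0.113 | 0.113 |
| AR(1) 0.8 | 1.62 | 0.124 | 0.125 |
| AR(1) 0.9 | 1.71 | 0.134 | 0.133 |
| Baseline .6 with each later month, later months .85 with each other | 1.45 | 0.104 | not run |
| Participant effect + AR(1) + month-specific noise (20–40% of variance) | varies | 0.056–0.083 | not run |
| Equal correlation .6, baseline SD 0.7 of later SDs | 0.90 | 0.039 | not run |

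For the last row: Var(V4 − baseline) = 0.49 + 1 − 2 × 0.42 = 0.65; mean variance = 3.49/4 = 0.8725; mean covariance = (0.42 + 0.60)/2 = 0.51; r = 0.65/(2 × 0.3625) = 0.90.

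At 17 per arm the simulated AR(1) results were nearly the same: 0.092 at 0.5 and 0.132 at 0.9.

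**Five time points (Visit 5 included).** For AR(1) 0.5 to 0.9, the baseline-to-Visit-4 error is 0.081 to 0.105 and the baseline-to-Visit-5 error is 0.092 to 0.150.

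**Two time points.** The mean correlation is the only correlation, so r = 1 and the error is 0.050 whatever its value.

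**Unstructured covariance.** On complete data this is the two-sample t-test on change from baseline. Its simulated error was 0.048 to 0.052 in every setting tried.

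**The case against.** A reader might infer that the plan commits to compound symmetry and that its secondary tests are therefore falsely significant about twice as often as intended. The documents do not support either step.

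- **The structure is left open.** The plan says the random effects include participants; it does not say intercept only or independent residuals. The sentence on residual covariance concerns these same continuous models and leaves room for another structure. This stands: compound symmetry is what results from coding the one device named, not a stated commitment. It does not remove the problem, because naming no structure leaves the choice to be made after the data are seen.
- **The size is not derivable.** A doubling needs a particular decay pattern. Large month-specific noise gives only 0.056 to 0.083. Equal correlation with a smaller baseline SD is conservative, and the entry floor of mean pain 4/10 (section 5.1) could shrink that SD. This stands, with one limit: a smaller baseline SD does not cancel unequal correlation. With baseline SD 0.7, correlation .5 with later months and .8 among them, the error is 0.089.
- **Not every outcome fits the four-point calculation.** The questionnaires run to Visit 5, where the baseline-to-Visit-4 inflation is smaller. PGIC is itself a rating of change. QST is measured at two visits and is unaffected.
- **The simulations used complete data.** The fix has not been tested under the planned dropout, and other pre-specified structures or robust standard errors could also serve.

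**Conclusion.** The point holds in a conditional form. For continuous secondary outcomes with several monthly assessments, section 12.3 names one correlation device and chooses no residual structure or degrees-of-freedom method. If a random intercept with independent residuals is fitted, the nominal 5% baseline-to-Visit-4 test has a true error of about 6% to 13% under the unequal-correlation patterns tried. It is exact under equal correlation and about 4% with equal correlation and a smaller baseline SD. With Visit 5 in the model, AR(1) 0.5 to 0.9 gives about 8% to 10% for Visit 4 and 9% to 15% for Visit 5.

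These figures rest on assumed correlations and complete data. They say nothing about the binary primary test or outcomes measured at two visits. Because this is a cheap, standard correction to secondary analyses, it is worth making before unblinding.

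**What to change.** In section 12.3, for continuous outcomes with three or more time points, replace the participant random effect with a repeated-measures model with unstructured covariance across the scheduled time points, fitted by REML with Kenward-Roger degrees of freedom. Name heterogeneous Toeplitz as the fallback if the model does not converge.

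The cost is SAP wording and a REPEATED statement in SAS, which is already the stated software. On complete four-point data, the degrees of freedom for the contrast fall from (40 − 2) × 3 = 114 to 40 − 2 = 38, and the critical value moves from about 1.98 to 2.02. That alone widens intervals by about 2% (2.02/1.98). Where correlation decays, they widen further by roughly √r, which is the correction intended.

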3.2.2 Secondary

Efficacy will be investigated further using secondary outcomes:

Secondary outcome measures will be a comparison with placebo of reduction of pain score from baseline continuously through to the end of 12 weeks (Visit 4).

Assess the efficacy of Erenumab compared to placebo on the proportion of subjects who achieved a least 30% reduction in the monthly average daily pain score from baseline to Visit 5 (follow-up/final visit).

A change in participant ratings compared to placebo from baseline of other pain related outcomes using functional measures related to TNP impact in daily activities, disability and emotional functioning measured by questionnaires (GCPAs, HADS, PGIC and PENN Facial Pain Scale), assessed over the length of the study.

Functional measures related to TNP impact in daily activities, disability and emotional functioning:

Penn Facial Pain Scale-Revised: Change/improvement in burden/disability of daily activities related to trigeminal neuropathic pain (e.g. chewing, eating, talking, touching) [31].

Graded Chronic Pain Scale (GCPS): Changes in pain intensity and pain related disability [32]

Patient Global Impression of Change (PGIC): Assesses patient perspective of pain improvement [33].

Hospital Anxiety and Depression Scale: Change in Anxiety and depression [34].

Exploratory Endpoint

To investigate whether Erenumab decreases pro-inflammatory cytokine release and increase anti-inflammatory cytokine release

To investigate whether eremumab induces changes in nociceptive processing and sensitization determined with QST measurements. In patients with persistent trigeminal

neuropathic pain altered pain modulation is present. We will investigate if erenumab influences sensitization [35-38].

To investigate whether erenumab decreases pain sensitivity determined by PAF measurements during EEG assessment. In chronic pain patients, alpha rhythms are slower in frequency and elevated in power relative to matched, healthy controls [39, 40]. We have shown that PAF predicts future pain sensitivity in multiple experimental pain models [41-43]. We will examine whether erenumab can modulate PAF and therefore, influence pain sensitivity.

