7.2 Screening and Baseline Visit (Visit 0, 4 weeks period)

This visit will happen with 2 weeks after pre-screening. Participants will start the baseline period that will consist of 4 weeks.

- Obtain and document consent from subject participation in the study.
- Obtain signed Health Insurance Portability and Accountability Act (HIPAA)

Authorization

- Review medical/dental history to determine eligibility based on inclusion/exclusion criteria.
- Take blood pressure and collect weight and height.
- Review medications history to determine eligibility based on inclusion/exclusion criteria.
 - Record concomitant medications and therapies
- Perform QST examination
- Perform EEG
- Collect blood for Cytokine release assay

- - Perform urine pregnancy test (in women with childbearing potential)
 - Provide instruction to complete 4 outcome measure questionnaires in paper or electronically for review next visit
 - Provide instruction to complete Daily Symptom Diaries electronically or in paper dispense forms.

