7.3.1 First treatment cycle (Visit 1, Day 0)

- Review Daily Symptom Diaries in eCRF or collect and review it in paper forms
- Review medical/dental history to determine eligibility based on inclusion/exclusion criteria.
- Record concomitant medications and therapies
- Take blood pressure and collect weight
- Assess and record adverse events (AEs)
- Perform urine pregnancy test (in women of childbearing potential)
- Review 4 questionnaires from Visit 0 in eCRF or collect and review the paper forms

- Provide instruction to complete 4 new outcome measure questionnaires in paper or electronically for review at Visit 2.
- Provide instruction to complete Daily Symptom Diaries electronically or provide them in paper forms
- Deliver the injection of the study drug or placebo
- Schedule next visit

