- Penn Facial Pain Scale-Revised: Brief 12 item questionnaire (the higher the score the more pain and disability) to assess burden and restrictions of daily activities in patients with trigeminal neuralgia (e.g. chewing, eating, talking, touching) and assess and monitor the impact of treatment interventions [31].
- Graded Chronic Pain Scale (GCPS). The GCPS includes 7 items and assesses 2 dimensions of pain: pain intensity and pain-related disability [32].
- Patient Global Impression of Change (PGIC). This instrument measures change
 in participant's overall status on a scale ranging from 1 (very much improved) to 7
 (very much worse). The PGIC is based on the Clinical Global Impression of
 Change, which is a validated scale [33, 46].
- Hospital Anxiety and Depression Scale. Evaluates anxiety and depression with a 14-item instrument [34].

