APPENDIX A: SCHEDULE OF EVENTS

Study Phase	Pre-	Screening	Randomization ^B and Treatment				Follow	Early
, and the second	screening ^A	and	(12 weeks of treatment/3 cycles				Up	termination
	_	Baseline	of Erenumab)					
Clinic Visit		V0	V1 ^c	V2	V3	V4	V5	ET
Study Day/	0-2 weeks	4 weeks	Day 0	Day	Day	Day	Day	
	prior to V0	prior V1		28	56	84	112	
Procedures								
Contact	Х							
Information								
Pre-screening	Х							
interview Script								
Informed		Х						
consent ^D								
Eligibility	Х	Х						
Review								
Demographic		Х						
information								
Medical history	Х	Х	Х	Х	Х	Х	Х	Х
and Review								
Concomitant		Х	Х	Х	Х	Х	Χ	Х
medications								
Concomitant		Х	Х	Х	Χ	Х	Х	Х
therapies								
Adverse Event			Х	Х	Х	Х	Х	Х
Review								
Dispense Daily		Х	Х	Х	Х	Х		
Symptom								
Diaries ^E								
Collect Daily		Х	Х	Х	Х	Х	Χ	
Symptom								
Diaries ^E								
Assess		Х	Х	Х	Х	Х		
compliance								
with Daily								
Symptom								
Diaries								
Provide study			Х	Х	X			
drug injection ^F								

Study Phase	Pre- screening ^A	Screening and Baseline	Randomization ^B and Treatment (12 weeks of treatment/3 cycles of Erenumab)				Follow Up	Early termination
Clinic Visit		V0	V1 ^c	V2	V3	V4	V5	ET
Study Day	0-4 weeks	1-3 weeks	Day	Day	Day	Day	Day	
	prior to V0	prior V1	0	30	60	90	120	
Clinical		-						
Examination								
and Tests								
Weight		Х	Х	Х	Х	Х	Х	Х
Height		Х						
Vital signs		Х	Х	Х	Х	Х	Х	X
Urine		Х	Х	Х	Х	Х	Х	X
pregnancy test								
QST		Х				Х		
EEG		Х				Х		
Schedule next	Х	Х	Х	Х	Х	Х		
visit								
Laboratory								
Blood draw for		Х				Х		
Cytokine								
release assay								
Questionnaires								
Symptom		X	Х	Х	Х	Х	Х	Х
Inventory								
Graded Chronic		Х	Х	Х	Х	Х	Х	Х
Pain Scale ^G								
Penn Facial		X	Х	Х	Х	Х	X	Х
Pain Scale-								
Revised ^G								
Patient Global		Х	Χ	X	X	Х	Х	X
Impression of								
Change ^G								
Hospital Anxiety		X	Χ	X	X	X	X	X
and Depression								
Index ^G								

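### PGIC is already a rating of change, yet it is collected before treatment and grouped with outcomes tested as change from baseline; its role and analysis need restating.

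*Combined protocol and SAP*

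**What the plan says.** Section 8.1 describes PGIC as measuring change "in participant's overall status on a scale ranging from 1 (very much improved) to 7", where 7 is very much worse. It names no time point against which the change is judged.

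Appendix A marks PGIC at Visits 0 to 5 and at early termination. Section 7.2, for Visit 0, reads "Provide instruction to complete 4 outcome measure questionnaires in paper or electronically for review next visit". Section 7.3.1, for Visit 1 (the first injection), reads "Review 4 questionnaires from Visit 0 in eCRF or collect and review the paper forms". The same pattern continues: forms issued at Visits 1, 2, 3 and 4 are reviewed at Visits 2, 3, 4 and 5.

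Section 3.2.2 introduces the questionnaire outcomes as "A change in participant ratings compared to placebo from baseline of other pain related outcomes" and names PGIC in that list with GCPS, HADS and the Penn scale.

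Section 12.3 tests the primary endpoint by the group-by-time interaction from baseline to Visit 4. It then gives the other secondary objectives linear mixed models, adding "The model and testing will be the same as described in the above primary objective". It restricts those models to continuous outcomes and does not name PGIC among the examples. A later paragraph of 12.3 lists PGIC with demographics and rescue medication, as data to be described and possibly used as covariates.

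**The concern.** A participant completing PGIC during the untreated baseline period has no treatment-related change to report and is not told what to compare with. Used as a baseline, that answer is subtracted from the rating of interest. For each participant the result is a change in a change rating, which is hard to interpret and may be noisier than the post-treatment rating alone.

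The plan also gives PGIC two incompatible roles. Sections 3.1, 3.2.2 and 12.1 make it a secondary efficacy measure, while 12.3 lists it as a possible covariate. If a post-treatment PGIC were used to adjust another efficacy model, that model would be adjusting for a consequence of treatment.

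At stake is one of four secondary questionnaires. The primary endpoint is not affected.

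**Working it through.** **1. The plan's own figure.** The documents give no sample size, power, SD, correlation or effect for PGIC. The nearest figure is section 12.2's n = 36 (18 per arm) for the primary endpoint, with d = 0.8, two-sided alpha 0.05 and power above 80%. A two-sample t test with those inputs has 64.5% power, so the stated power is not reproduced. That is a separate matter. Here d = 0.8 and 18 per arm serve only as a common yardstick.

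**2. What the interaction estimates.** With complete data, the Visit 4 versus baseline group-by-time term is the difference between arms in mean (Visit 4 − Visit 0). The Visit 0 rating precedes the first dose in a randomised, blinded trial, so its expected value is the same in both arms and cancels. The interaction and the direct Visit 4 comparison therefore have the same expected value and can differ only in variance.

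**3. Variance and power.** Let r = SD at Visit 0 / SD at Visit 4, and let ρ be the correlation between the two ratings. Relative to the direct comparison:

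- variance factor = 1 + r² − 2ρr
- effective d = 0.8 / √(1 + r² − 2ρr)
- precision is lost only if 1 + r² − 2ρr > 1, that is, if ρ < r/2.

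Power by the noncentral t distribution, 18 per arm, two-sided 0.05:

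| Analysis | r | ρ | Variance factor | Effective d | Power |
|---|---|---|---|---|---|
| Direct, Visit 4 | – | – | 1.00 | 0.800 | 64.5% |
| Interaction | 0.5 | 0 | 1.25 | 0.716 | 55.0% |
| Interaction | 1.0 | 0 | 2.00 | 0.566 | 37.8% |
| Interaction | 0.5 | 0.3 | 0.95 | 0.821 | 66.7% |
| Interaction | 1.0 | 0.3 | 1.40 | 0.676 | 50.4% |
| Interaction | 1.0 | 0.5 | 1.00 | 0.800 | 64.5% |
| Interaction, all Visit 0 answers identical | 0 | – | 1.00 | 0.800 | 64.5% |

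**4. Check on the real scale.** Ratings were simulated on a rounded 1 to 7 scale at 20 per arm, with placebo mean 3.6, SD 1.3 and difference 1.04 (0.8 × 1.3). The direct comparison had about 67% power. The change score had 67% when all Visit 0 ratings were 4, 46% with Visit 0 SD 1 and ρ = 0, 38% with SD 1.3 and ρ = 0, and 68% with SD 0.5 and ρ = 0.3. The pattern is the same.

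**5. Which form is which.** Section 7 describes five sets of forms, issued at Visits 0 to 4 and each reviewed at the next visit.

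- Labelled by review visit, the Visit 4 PGIC is the form issued at Visit 3. It covers the last treatment cycle.
- Labelled by issue visit, it is the form reviewed at Visit 5. It covers follow-up.

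Appendix A's marks do not show which is meant. The questionnaire rows carry a footnote whose text is not in the copy reviewed.

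**The case against.** The strongest reply is that the documents never say outright that PGIC enters the mixed model. Section 12.3 confines those models to continuous outcomes, PGIC is a single seven-point item, and the later paragraph treats it as descriptive. The 3.2.2 sentence also covers four questionnaires at once, and in the item list below it PGIC is the only one not described as a change in something. This stands in part: the interaction test for PGIC is an inference. It does not rescue the plan. If the mixed model does not apply, a named secondary efficacy outcome has no inferential analysis; if it does, the Visit 0 rating is subtracted.

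A reader might go further in three ways that the documents do not support.

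- *The PGIC comparison is biased or meaningless.* It is not biased: the pre-treatment rating has equal expectation in both arms, so the contrast keeps the meaning of the direct comparison. What is hard to interpret is the individual difference score.
- *Power is necessarily lost.* It is lost only when ρ < r/2. At r = 0.5 and ρ = 0.3 there is a slight gain (66.7% against 64.5%), and an untreated group may well mostly answer that nothing has changed.
- *The Visit 1 form is also pre-treatment and should go.* It is issued at the first injection visit and reviewed at Visit 2, so it may be completed after dosing. Removing it could discard the first on-treatment rating. Only the Visit 0 form is clearly pre-treatment.

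**Conclusion.** The point holds as a defect in how a secondary outcome is specified. A change rating is collected before treatment without a reference point, grouped with outcomes measured as change from baseline, and given conflicting roles in 12.3. No section gives it an analysis suited to its form.

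The treatment contrast is not biased. The possible cost is precision: from no loss, or a small gain, down to 38% power against 64.5% in the worst case considered (equal SDs, no correlation). These figures rest on d = 0.8 borrowed from the primary endpoint and on assumed SD ratios and correlations. They show a range and do not predict what the trial will lose.

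The correction should be made because it is cheap and the direct comparison is plainly the better analysis. It does not bear on the primary result.

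**What to change.** 1. Drop PGIC at Visit 0, and state on the form and in section 8.1 that change is judged from the start of treatment.
2. In section 3.2.2, take PGIC out of the change-from-baseline wording and define it as the post-treatment rating compared between arms.
3. In section 12.3, prespecify a direct comparison of arms on the PGIC covering the last treatment cycle. Use an ordinal model or a rank test, or a repeated-measures model of the post-baseline ratings with no baseline term. Remove PGIC from the possible covariates.
4. State which form counts as Visit 4, given that forms issued at one visit are reviewed at the next, and align Appendix A with section 7. Keep the form issued at Visit 1 unless it is confirmed to be completed before dosing.

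The cost is protocol and SAP wording and one fewer questionnaire per participant. No participants, visits or procedures are added.

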12 STATISTICAL CONSIDERATIONS

12.1 Study Hypotheses

The primary efficacy hypothesis is a higher proportion of participants in Erenumab group will achieve at least 30% reduction in monthly average pain score from baseline (monthly data prior to Visit 1) to end of treatment (monthly data prior to Visit 4) than those in placebo group.

The secondary efficacy hypothesis:

To investigate the efficacy of Erenumab compared to placebo on the reduction in monthly average daily pain score from baseline to the end of 12-week treatment period.

To investigate the efficacy of Erenumab compared to placebo on the proportion of subjects who achieved a least 30% reduction in the monthly average daily pain score from baseline to Visit 5 (follow-up/final visit).

To determine the efficacy of Erenumab using functional measures related to TNP impact in daily activities, disability and emotional functioning measured by questionnaires (GCPAs, HADS, PGIC and PENN Facial Pain Scale).

The exploratory hypothesis:

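### Section 12.3 allows PGIC, a secondary efficacy outcome, as an optional covariate without limiting it to pre-dose values; separately, the continuous secondary models leave baseline unadjusted

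*Combined protocol and SAP*

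**What the plan says.** Section 12.3 gives the fixed effects of the primary model as "treatment group (intervention versus placebo), time (dummy coded from baseline to visits 2-4), and the interaction terms of group by time", with a random participant effect. For the continuous secondary outcomes, "The model and testing will be the same as described in the above primary objective". Neither model has a covariate. Baseline is one level of time, and nothing makes the arms share a baseline mean.

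After a line on descriptive safety statistics, the section adds that some data are collected for description and, "if necessary, to use as covariates: Demographic information (age and race/ethnicity), rescue medication history, psychological factors and perceived change in overall status (PGIC". It gives no criterion for necessity, no model and no visit. Covariates are tied to baseline only in the Missing Data paragraph, which would consider "sensitivity analyses that add these relevant baseline covariates to make the MAR assumption more plausible" if dropout is informative.

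Sections 3.1, 3.2.2 and 12.1 make PGIC a secondary efficacy outcome; section 3.2.2 has it "measured by questionnaires (GCPAs, HADS, PGIC and PENN Facial Pain Scale), assessed over the length of the study" and describes it as the patient's view of pain improvement. Section 8.1 describes a rating of change in "overall status on a scale ranging from 1 (very much improved) to 7", where 7 is the worst end.

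On timing, section 7.2 issues the four questionnaires at Visit 0. At Visit 1, when the first injection is given, section 7.3.1 says "Provide instruction to complete 4 new outcome measure questionnaires in paper or electronically for review at Visit 2". The pattern continues, so sets issued at Visits 1 to 4 are reviewed at Visits 2 to 5. Appendix A marks PGIC at V0 to V5 and at early termination.

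**The concern.** A covariate that treatment can change is not a safe adjustment variable. PGIC overlaps the pain endpoints, so adjusting a pain comparison for on-treatment PGIC asks what erenumab does among people who report the same improvement. That is no longer the full treatment effect.

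Two other listed items carry a similar risk if taken after dosing. Rescue use is quantified at each visit (section 6.6.1.2). Psychological factors are undefined; if HADS is meant, that too is a secondary outcome. Age and race/ethnicity raise no timing problem. The missing trigger also matters in itself, because the choice of covariates could follow sight of the results.

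The second matter is precision. In a 40-person trial, the continuous secondary comparisons do not use the baseline score as efficiently as they could.

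**Working it through.** The plan gives no figure for either matter. The only input taken from it is the effect size in section 12.2, d = 0.8 or OR 4.2, used as a scale. Its rates agree: odds of 0.25/0.75 times 4.2 give 1.4, and 1.4/2.4 = 58.3%, against the stated 58%. All correlations and causal structures below are assumptions; the documents give none.

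**1. PGIC as covariate (continuous score, one visit, unit SDs).** Adjusted effect = d − r × (shift in PGIC), where r is the within-arm correlation.

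| Assumption | Formula | r = 0.3 | r = 0.5 | r = 0.7 |
|---|---|---|---|---|
| PGIC moves only through pain (shift = r·d) | d(1 − r²) | 0.73 | 0.60 | 0.41 |
| Share of effect lost | r² | 9% | 25% | 49% |
| PGIC has the same standardised effect (shift = d) | d(1 − r) | 0.56 | 0.40 | 0.24 |
| Share of effect lost | r | 30% | 50% | 70% |
| Drug does not move PGIC (shift = 0) | d | 0.80 | 0.80 | 0.80 |

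**2. On-treatment rescue use.** Take a true total effect of −0.60, severity U with variance 1 and noise with variance 1.
- Rescue relieves pain: R = −0.5T + sU + noise and Y = −0.8T + U − 0.4R. Total effect = −0.8 + 0.4 × 0.5 = −0.60. Adjusted effect = −0.8 + 0.5s/(1 + s²), which is −0.80/−0.66/−0.58/−0.55 at s = 0/0.3/0.6/0.9.
- Rescue only marks pain: Y = −0.6T + U and R = sY + noise. Adjusted effect = −0.6/(1 + s²), which is −0.55/−0.44/−0.33 at s = 0.3/0.6/0.9.

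The estimate can therefore move in either direction.

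**3. What the planned continuous contrast is.** In one simulated complete dataset (18 per arm, four time points), the group-by-time term at the last visit was −0.17762 from a random-intercept model and −0.17762 from generalised least squares with an unstructured covariance. The plain difference in mean change was also −0.17762; ANCOVA gave −0.19094. With complete data, the planned contrast is the unadjusted difference in mean change.

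**4. Precision available.** Let k = baseline SD / Visit 4 SD and rho the baseline-to-Visit 4 correlation. Variance of a change = 1 + k² − 2·rho·k; variance after baseline adjustment = 1 − rho². The ratio is (1 − rho²)/(1 + k² − 2·rho·k), which reduces to (1 + rho)/2 at k = 1.

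| rho | 0.3 | 0.5 | 0.7 | 0.8 |
|---|---|---|---|---|
| k = 1 | 0.65 | 0.75 | 0.85 | 0.90 |
| k = 0.7 | 0.85 | 0.95 | 1.00 | 0.97 |
| Simulated ANCOVA, 20 per arm, k = 1 | 0.66 | 0.77 | 0.87 | 0.93 |
| Simulated ANCOVA, 20 per arm, k = 0.7 | 0.88 | 0.97 | 1.03 | 1.00 |

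The k = 0.7 rows illustrate the pain score, whose baseline SD may be narrowed by the entry floor of 4/10 (section 5.1, criterion 5). There the extra parameter can cost about as much as it gains.

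**The case against.** The strongest reply is that nothing planned is affected. The covariate sentence puts description first, and the specified models contain no covariate. Harm needs three further steps: the option is used, on-treatment values are entered, and the adjusted result replaces the specified one. No section plans any of them. This stands, and it makes the harm conditional.

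Next, a pre-dose PGIC exists. That is also true, so it would be wrong to say that PGIC is rated only after dosing. The accurate criticism is that the sentence does not restrict use to the pre-dose value. A change rating given before treatment also cannot describe response to the study drug. Likewise, rescue medication history may mean prior use, but the text does not say so.

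On the second matter, the planned contrast is valid under randomisation, so baseline adjustment is an improvement rather than a correction. A single-visit ANCOVA would also drop participants without Visit 4 data, whose other visits the mixed model keeps, and section 12.2 expects 15% dropout. Both points stand and shape the fix.

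Four stronger readings are tempting but unsupported:
- That the primary test will be adjusted for PGIC. The default model excludes it.
- That the open option puts the false-positive rate at 12 to 18%. That is a worst case: the most favourable of all 32 subsets of five independent continuous covariates, correlated 0.2 to 0.3 with the outcome. With one optional covariate the rate is about 6%.
- That the continuous models take change scores as the response. They model the scores themselves; only the tested contrast is equivalent to a change comparison, and this was shown for complete data.
- That baseline adjustment would help the binary primary endpoint. No such gain is claimed.

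**Conclusion.** The concern holds in a limited form. Section 12.3 permits adjustment for an efficacy outcome without a trigger or a limit to pre-dose values. If on-treatment PGIC were used and erenumab moves PGIC, the estimate would be too small. The loss is 9/25/49% in the through-pain case, larger if PGIC responds equally in its own right, and nil if PGIC does not respond. These sizes come from a single-visit linear model with assumed correlations, not from the planned mixed models. For on-treatment rescue use the direction of bias cannot be stated.

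The baseline matter is a free gain in precision for continuous secondary scores. Its size depends on the unknown rho and k, and for monthly mean pain it could be close to nothing. The case for amending the plan rests on the covariate sentence.

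**What to change.** In section 12.3:
- Delete PGIC from the covariate list. Keep it as a secondary outcome, compared directly between arms at post-dose visits including Visit 4, rather than as a change from Visit 0.
- Replace the open-ended condition with covariates named in advance, the model each enters, and a statement that all are measured before the first dose (for example Visit 0 HADS, or medication use before Visit 1).
- For scores with a true baseline (monthly mean pain, Penn, GCPS, HADS), keep the longitudinal mixed model but constrain the arms to a common baseline mean. Alternatively, model the post-baseline visits with the baseline score as a covariate. Test the group contrast at Visit 4. Do not use a single-visit ANCOVA.

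The responder model needs no added baseline covariate on account of this point. The cost is analysis-plan wording, best settled before unblinding. No new data are needed: the Visit 0 questionnaires, prior medication and baseline diary are already collected.
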